7.1.1 Handling of missing values/censoring/discontinuations

Patients who withdraw early before receiving the second/third dose and a follow-up MRI may be replaced. Missing data will not be imputed and left missing for statistical analyses.

7.1.2 Supportive analyses

Part A, Part B and Part C pooled for weeks 1 to 4 (Part A*)

As a supportive analysis, log ratio to baseline of tumor volume at week 4 may be subjected to an Analysis of Covariance (ANCOVA) model. The model will include log transformed tumor volume at baseline and a factor for treatment. Point estimates and 95% confidence interval will be calculated for MCS110 and Placebo separately, and for the difference of means between MCS110 and Placebo. Results will then be transformed back to the original scale.

Part B*:

To study the time course of tumor volume reduction from baseline, a repeated measures ANCOVA model on log ratio to baseline will be fit by resetting the tumor volume at week 4 as baseline for patients in treatment group 2 and the visit number will be adjusted accordingly. The model will include log tumor volume at baseline and visit as fixed effects. Standard fit statistics will be used to determine the best variance-covariance structure. Point estimates and 95% confidence interval will be calculated at each visit. Baseline adjusted tumor volume (+/- SE) over time will be plotted.

Part C:

As a supportive analysis, log ratio to baseline of tumor volume at week 4 may be subjected to an Analysis of Covariance (ANCOVA) model. The model will include log transformed tumor volume at baseline and a factor for treatment. Point estimates and 95% confidence interval will be calculated for each treatment arm and for the difference of means between treatment groups. Results will then be transformed back to the original scale.

The statistical analysis will also be provided by age group (<18 years and ≥18 years).

Parts A, B and C :

A dose-time-response model (Lange and Schmidli 2015) will be used to analyze tumor response data (log ratio to baseline of tumor volume) from Parts A, B, and C. The following equation will be used for the latent concentration $C(t)$ of a patient who receives K doses with dose D_k received at time t_k , $k=1, \dots, K$:

$$C(t) = \sum_{k=1}^q \frac{D_k \theta_1}{\theta_1 - \theta_2} \left\{ \exp \left[-\theta_2 \left(t - \sum_{j=0}^{k-1} \delta_j \right) \right] - \exp \left[-\theta_1 \left(t - \sum_{j=0}^{k-1} \delta_j \right) \right] \right\}$$

where $\delta_0=t_1$, $\delta_j=t_{j+1} - t_j$ for $j=1, \dots, K-1$ and $q \in \{1, \dots, K - 1\}$ is such that $t_q < t \leq t_{q+1}$ and $q=K$ if $t > t_K$.

The above latent equation will be substituted in the equation below which will be used to model the dose response:

$$y_{ij} = a + \frac{\theta_4 C(t)}{\theta_3 C(t)} + \epsilon_{ij}$$

where $\epsilon_{ij} \sim N(0, \Sigma)$ i.i.d are the residuals. The observations will be considered to be independent between patient but dependent within a patient.

Preliminary results of the Placebo group have shown that a Placebo time-changing response may have been observed. To adjust for that the a term may be replaced with $\sum_{r=5}^R \theta_r \gamma_r(t)$, where θ_i are unknown real-valued parameters and the $\gamma_i(t)$ are arbitrary real valued known functions (which will be decided at that time).

The model will include tumor at baseline as a covariate (baseline will be centered) but other demographic/baseline variables may also be added. A random effect may also be considered if the data permits.

Only post-baseline values will be considered for the analysis.

Time-dose-response models describe and predict drug effect for complex dosing regimens. The mechanistic non-linear regression model above will allow for both inference on model parameters and prediction of the time-changing tumor response for the dosing regimens used in this study. Mechanistic models are based on prior knowledge and provide more reliable predictions. To this end, a Bayesian approach (using prior information) with weakly informative prior will be used. Point estimates and 95% confidence intervals of the model parameters, i.e., the expected response after multiple doses, will be generated using the Emax model. The Emax model will estimate tumor reduction from baseline at each dose and timepoint. Dose-time-response curves based on the model will be generated and graphically presented. The pooled dataset should result in approximately 19 patients on 10mg/kg, 6 patients each on 3 and 5 mg/kg (up to 10 if a lower efficacious dose is identified), and 5 patients (2 in Part A and 3 as first dose in Part B) on placebo.

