9.4 Analysis of the primary variable

9.4.1 Variable(s)

Part A:

The tumor size (volume) as assessed by MRI technique up to and including week 4 will be the primary measure of efficacy. The tumor size at baseline and at week 4 will be log transformed. The log ratio to baseline of the tumor size (change from baseline of log transformed volume) will be the primary endpoint.

Part B:

The tumor volume will continue to be the primary measure of efficacy. In particular, if the tumor is too small to be measurable at follow-up, it is considered as complete response.

Part C:

The tumor volume will continue to be the primary measure of efficacy. In particular, if the tumor is too small to be measurable by MRI, it is considered as complete response.

Tumor volumes will be listed and descriptively summarized at each MRI assessment time by MCS110 dose group (3 mg/kg, 5 mg/kg, 10 mg/kg). Moreover, the number and percentage of patients with complete tumor response (CR) will be presented, and the time that the complete tumor response is observed will be listed by patient and dose group. In addition, incidences of patients with partial response (PR), stable disease (SD) and progressive disease (PD) will be listed by dose group.

Tumor volume reduction after 3 doses, evaluated by week 12 MRI, will guide the decision on whether to continue with the initial dosing (3 mg/kg or 5 mg/kg) or increase the dose to 10 mg/kg for the following doses.

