9.4.4 Supportive analyses

Part A

As a supportive analysis, log ratio to baseline of tumor volume at week 4 may be subjected to an Analysis of Covariance (ANCOVA) model. The model will include log transformed tumor volume at baseline and a factor for treatment. Point estimates and 95% confidence interval will be calculated for each treatment group and for the difference of means between treatment groups. Results will then be transformed back to the original scale.

Part B

To study the time course of tumor volume reduction from baseline, a repeated measures ANCOVA model may be fit by resetting the tumor volume at week 4 as baseline for patients in treatment group 2 and the assessment time will be adjusted accordingly. The model will include tumor volume at baseline and assessment time (in month) as fixed effects. Standard fit statistics will be used to determine the best variance-covariance structure. Point estimates and 95% confidence interval will be calculated at each assessment time-point and between different assessment time-points.

Part C

As a supportive analysis, log ratio to baseline of tumor volume at week 4 may be subjected to an Analysis of Covariance (ANCOVA) model. The model will include log transformed tumor volume at baseline and a factor for treatment. Point estimates and 95% confidence interval will be calculated for each treatment arm and for the difference of means between treatment groups. Results will then be transformed back to the original scale.

Parts A, Part B and Part C

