Decision Rule

The PoC criterion is two-fold, as follows:

- $\text{Prob}(LR(\text{treated}) < LR(\text{placebo})) > 0.90$; i.e. 90% confidence in superiority to placebo
- $\text{Prob}(LR(\text{treated}) - LR(\text{placebo}) < \log(0.6)) > 0.50$; i.e. 50% confidence in the treated group ratio being 40% below the placebo group ratio

[figure not shown]
At least one placebo patient and two MCS110 patients must be included to declare PoC. Both neutral and skeptical priors will be used to assess the PoC criterion. The skeptical prior is used to shift prior beliefs toward no effect of MCS110 i.e. stronger evidence from the data in favor of MCS110 will be needed to reach PoC. The skeptical analysis will only be run as a sensitivity analysis.

Once the PoC criterion is reached, the clinical trial team (CTT) may decide to continue recruitment to collect more data on MCS110.

If after 6 patients have completed the 4 week treatment, the PoC criterion is not reached, the probability to reach PoC with the addition of 6 new patients will be assessed, and if this probability is less than 10% the trial may be stopped for futility.

For illustration, an example of a trial path simulation with skeptical and neutral priors on mean treatment effect in MCS110 group is shown below ([Figure 7-1](#)):

Figure 7-1 Example of a sample path

The left plot displays the skeptical analysis and the right plot the neutral analysis.

The blue dots represent the posterior mean in the MCS110 group and the black dots represent the posterior means in the placebo group as more patients contribute data.

The green dots show the probability of MCS110 being superior to placebo, and the pink dot the probability to be better by 40%.

In this example, the PoC criterion is reached after 3 patients when neutral prior (second graph) is used, and after 4 patients when skeptical prior (first graph) is used.

The posterior probability of LR(treated), LR(placebo) and their difference will be estimated using MCMC techniques using at least 40000 simulations discarding a sufficient number of the initial samples to insure convergence of the markov chain (based on trace plot visual inspections).

In the event that there are any complete responders a square root ratio analysis will be performed instead. In this analysis everything else will be the same as above other than using square root ratio instead of log ratios.

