The same model as above will also be applied to compare the efficacy of the 3 mg/kg and 5 mg/kg to the 10 mg/kg dose (instead of Placebo).

Part B and C (referenced as Part B* hereafter)

Part B includes all data from multiple dosing Parts. In Part B, treatment group 1 = MCS110 throughout the trial, treatment group 2 = Placebo for the first dose and MCS110 from the second dose. In Part C, treatment arm 1 = MCS110 3 mg/kg, treatment arm 2 = MCS110 5 mg/kg, treatment arm 3 = MCS110 10 mg/kg, for patients in treatment arms 1 and 2 that switch to 10 mg/kg after 3 doses, they will be included in their original treatment group for the first 3 doses and will added in a separate group after that (4= MCS110 3 mg/kg for 3 doses and 10 mg/kg afterwards and 5= MCS110 5 mg/kg for 3 doses and 10 mg/kg afterwards), no re-calculation of baseline will occur for the people who change treatments.

Tumor volumes will be listed at each MRI assessment timepoint till the end of the study by treatment groups.

Part B*: MCS110 data only, by including data starting from the 1st dose of MCS110 in all treatment groups of Parts B and C. More specifically, for Part B treatment group 2, the measurement right before patients receiving the first dose of MCS110 (2nd dose from screening) will be treated as the new baseline and assessment time-points will be adjusted accordingly. Summary statistics of the consolidated tumor volume for the raw values, percent change and absolute change from baseline.

Arithmetic mean (+/-) SE on percent change from baseline vs time plot will be produced for Part B*. Waterfall plot of the maximum reduction until 8 Weeks after last dose will be produced in regards of number of doses received.

Overall Time to complete tumor ablation will be summarised up to the primary endpoint (8 weeks after the last MCS110 dose), along with a summary of overall time to $\geq 50\%$, and $\geq 80\%$ ablation. The number and frequency of patients reaching each level will also be included in the summary.

Overall Time to complete ablation is the time (in weeks) - from first MCS110 dose to the first time when there is no tumor detected. Overall time to $\geq 50\%$, and $\geq 80\%$ ablation is the time from first MCS110 dose to reach maximum ablation of [50%, 80%) and [80%, complete) respectively.

Part C

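### The multi-dose tumour-volume models in SAP 7.1.2 use a log ratio that is undefined at a complete-response visit, and the SAP's own fallback for complete responders is not extended to them

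*SAP*

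**What the plan says.** **Response scale.** In SAP 7.1.2, for Part B* (all MCS110 data from Parts B and C, counted from the first active dose), "a repeated measures ANCOVA model on log ratio to baseline will be fit by resetting the tumor volume at week 4 as baseline". The dose-time-response model is to "analyze tumor response data (log ratio to baseline of tumor volume) from Parts A, B, and C".

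**Complete response.** Protocol 9.4.1 (Part C) states that "if the tumor is too small to be measurable by MRI, it is considered as complete response"; the Part B wording is nearly the same. SAP 7.1 measures time to complete ablation up to "the first time when there is no tumor detected". Neither document gives the volume to be recorded at such a visit.

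**Existing fallback.** At the end of the Part A* (weeks 1 to 4) Bayesian analysis, SAP 7.1 says: "In the event that there are any complete responders a square root ratio analysis will be performed instead". The next sentence ties this to the model described above it. SAP 7.1.2 neither repeats it nor refers to it.

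**Missing data.** SAP 7.1.1: "Missing data will not be imputed and left missing for statistical analyses".

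**Two readers.** SAP 7.1 consolidates the two readers' volumes by their geometric mean.

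**The concern.** The SAP's remedy covers the four weeks after the first dose, when complete response is least likely. It is absent after up to six doses, where complete ablation is the stated aim (Protocol synopsis, Part B; Protocol 1.4). At those later visits the best possible outcome has no value on the model's scale. If such visits are handled as missing, whether a value is lost depends on the outcome itself, so the bias has a direction: the estimated reduction is too small.

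The two models matter even as supportive analyses. Apart from SAP 7.1.2, the multi-dose volume analyses are descriptive, so these are the models that give interval estimates of multi-dose volume reduction. Without a written rule, the handling of complete responses would be chosen after the data are seen. The descriptive percent-change tables can show a complete response as -100%, so tables and models could also disagree.

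**Working it through.** The plan gives no figure on this point to reproduce.

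**1. Scale.** For baseline volume V0, log(0/V0) is undefined and sqrt(0/V0) = 0. With reader values of 0 and 5, the geometric mean is sqrt(0 × 5) = 0, so one reader finding no tumour is enough to make the consolidated volume zero.

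**2. Mean over available visits.** Inputs: 11 Part B and 18 Part C patients (Protocol 1.1, Study CMCS110X2201), so n = 29; the other patients at a 50% reduction, an assumption in line with the average of about 50% after three doses in Protocol 1.4. The number k of complete responders is also assumed, because no rate is documented.

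All-patient mean reduction = 1 - (1 - k/29) × 0.50. With complete-response visits dropped, it stays at 50%.

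| k | All patients | Visits dropped | Gap (points) |
|---|---|---|---|
| 1 | 51.7% | 50% | 1.7 |
| 2 | 53.4% | 50% | 3.4 |
| 3 | 55.2% | 50% | 5.2 |

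**3. Likelihood repeated-measures model.** A patient's earlier measurable visits stay in and inform the later means. This was simulated with 30 patients, six visits, 60 runs per setting and a multivariate normal likelihood with unstructured covariance. Assumed trajectories: geometric mean ratios falling from 0.65 to 0.32, a patient effect growing over time, and residual SD 0.2 on the log scale. Visits with a ratio below a threshold (0.05, 0.10 or 0.15) were called complete responses and set to missing. The true value is the geometric mean of the ratios before that step.

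| Complete response at last visit | True ratio | Available visits only | Likelihood model | Likelihood bias (points) |
|---|---|---|---|---|
| about 5% | 0.339 | 0.382 | 0.342 | 0.3 |
| about 14% | 0.339 | 0.453 | 0.350 | 1.1 |
| about 25% | 0.332 | 0.528 | 0.358 | 2.6 |

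All 30 patients contributed data in every setting. The bias is toward a smaller effect throughout, but much reduced. The dose-time-response model was not simulated.

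**4. Effect of the unstated choice.** Take 10% complete responses and a ratio of 0.50 in everyone else:

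- visits dropped: 0.50
- square root ratio, squared back: (0.9 × sqrt(0.50))² = 0.405
- complete response set to 1% of baseline, log scale: 0.50^0.9 × 0.01^0.1 = 0.338
- set to 0.1% of baseline: 0.50^0.9 × 0.001^0.1 = 0.269

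These summaries are not all the same quantity, but each could be reported as the model's mean ratio. The spread is wider than the bias in step 3.

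**The case against.** **Both models are supportive.** This stands. The main multi-dose analysis is descriptive and can hold a zero: raw, absolute and percent change, a waterfall plot, time to complete ablation and the number reaching it (SAP 7.1), and the number and percentage with complete response (Protocol 9.4.2). The goal of ablation is therefore reported directly, whatever happens in SAP 7.1.2.

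**No text orders deletion.** Also correct. The protocol treats an unmeasurable tumour as an outcome, not as missing, and the stored value is unknown. Loss of these visits is an inference from an undefined log together with the no-imputation rule. The absence of any rule remains.

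**Stronger readings that the documents do not support.**

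- A reader might infer that the best responders leave the models altogether. Only their complete-response visits would go.
- A reader might divide by the 11 Part B patients alone, giving 54.5%, 59.1% and 63.6% for 1, 2 and 3 complete responders, or gaps of about 5 to 14 points. Part B* pools Parts B and C, so 29 is the right denominator, and a simple mean over available visits is not the planned model.
- A reader might say that the SAP created the problem by leaving a percent-change scale set in the protocol. Protocol 9.4.4 says "The model will include tumor volume at baseline and assessment time (in month) as fixed effects" and names neither percent change nor any other transformation of the response for Part B.
- A reader might claim a known bias in theta4, the maximum-effect parameter. That has not been computed.

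**Conclusion.** The gap is real and of moderate severity. Both multi-dose models in SAP 7.1.2 are specified on a scale that fails at complete response, and a remedy already in the SAP stops short of them. If complete-response visits are lost, the estimated reduction is biased toward a smaller effect. The size is about 2 to 5 percentage points for a mean over available visits (1 to 3 complete responders among 29, others at 50%), and about 0.3 to 2.6 points for a likelihood model at 5% to 25% complete response under the assumed trajectories. With no complete responses there is no effect. The effect on theta4 is unquantified. The supportive week 4 ANCOVAs in SAP 7.1.2 share the gap, but are less likely to be affected.

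**What to change.** Amend SAP 7.1.2 before database lock:

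1. State that a complete-response visit is an observed value and is never treated as missing.
2. Define the consolidated value for an unmeasurable tumour, including the case where only one reader finds none.
3. Extend the square root ratio of SAP 7.1 to the Part B* repeated-measures model and the dose-time-response model if any complete response occurs.
4. As a sensitivity analysis, treat complete-response visits in the Bayesian dose-time-response model as left-censored at a stated measurability limit.

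Substituting a small constant on the log scale should not lead. Halving the constant multiplies the geometric mean ratio by 2^(-p), where p is the complete-response share: 0.93 at 3/29 and 0.83 at 3/11. Protocol 6.4.1 defines measurability by lesion dimensions at screening, not by volume, so the imaging CRO would have to supply the limit for item 4.

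The cost is a few lines of SAP text; SAP 1.2 counts a change of statistical model as minor. The downsides are a slightly less familiar scale, whose back-transformed mean is not a geometric mean ratio, and some dependence of the sensitivity analysis on the chosen limit, which running it will show.

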³ During the study 12-lead ECG's should be conducted prior to blood collection.

⁴ Dosing should occur within 8 days after site received MRI validation from the vendor, infusion duration 1hr +/- 10 mns.

⁵ Two sequencial MRIs will be carried out at this visit.

Corporate Confidential Information

⁷ PK Blood for MCS110: All post-dose samples to be taken after end of infusion. The "1 hr" time point should be taken immediately after the end of infusion.

⁶ These samples are not required to be taken fasting.

⁹ SAE reporting from time of signing informed consent until 30 days after subject has stopped study participation.

¹⁰ AEs to be reported from time of first study drug administration on Day 1 until study completion.

¹¹ Alcohol and drug screen, pregnancy test, hematology and clinical chemistry : screening results can be used at baseline if baseline is planned in the next 7 days following screening.

Corporate Confidential Information

¹⁵ Hematology and clinical chemistry for safety purpose will be analyzed locally before any dosing day. Any other visits saftey samples will be analyzed by the central lab

¹⁶ At week 12, after dosing, patient's treamtment will be unblinded.

If Day 1 treatment is placebo, Assessment Schedule B1 will be applied from the next visit.

If Day 1 treatment is MCS110 Assessment Schedule B2 will be applied from the next visit Corporate Confidential Information

¹⁸ For Part B1 patients, an unscheduled visit 8 should be planned 4 weeks after visit 8 (week 20) as administration day of dose 5.

For Part B2 patients, an unscheduled visit 7 should be planned 4 weeks after visit 7 (week 16) as administration day of dose 5.

¹⁹ Collection of these samples is discontinued as of 30-Aug-2016

²⁰ Visit 109 (Part B1) will not be performed if patients had visits optional dosing visits 116 and 117 (schedule B1)

²¹ Visit 208 (Part B2) will not be performed if patients had visits optional dosing visits 215 and 216 (schedule B2). Corporate Confidential Information

Assessment Schedule (Part B – re-dosing)

	RLP	redosing Screening									R	(edo	sin	g Tr	eatr	men	t											Redo	sing Fo	ollow-up visit	EoS
Visit Numbers	1	2		3	1	4	Τ		5			6	6			7	7				8		Γ		9			10	11	12 (optional) ¹³	777
Visit Numbers for Crned Programming ¹	301	302		30	3	304	4	3	05			30	-			30				-	08				309			310	311	312 (optional) ¹³	780
Weeks	-	-		1		2			4				3			1					16				20			24	36	48	60
Months									1			2	2				3				4		Γ		5			6	9	12	15

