Patients who completed visit 14 or 15 by the time Protocol Amendment 07 is approved, need to come back to the site within 1 month for an end of study visit to perform remaining assessments Corporate Confidential Information

Patients who did not yet achieve visit 14 or 15 by the time Protocol Amendment 07 is approved, need to follow Protocol Amendment 07 assessment schedule.

	CM	CS11	0X220	1 Pa	art	C - A	Ass	ess	me	nt S	Sch	edu	ule																		
	Scree	ning	Baseline	1										Trea	tmen	t											_	Follo	w-up		EoS
Visit Numbers [†]	1		2	-	3	_	4			5	_		6		 		7		—		R		—		2	-+	10			13	777
Viai Vultera Weeks			-	 	1					4	_				-		12		-	_	16		+		0	-				56	72
Weeks Months		-1			1					4	_	_	2		-		3		-		4		+		5	-+	6		10		18
				-	_				_		_				_				-				-			_					
Study Day	- 28 to -22	-21 to -8	-7 to -1	-	1		1	5		29	_		57		_		85		-		113		-		41	-	169	197	281		505
Allowed visit window (days)	-	-	-			1 - 1 -	±	3		±3			±5		_		±5		-		±5				5			±8		±8	±8
Time hrs	-	-	-	pre	0 1	2 :	5 -	pre	0	1 2	5	pre	0 1	2	5 pi	rero	1	2 :	pre	0	1	2 5	pre	0	1 2	5	-	-	-	-	-
Informed consent	×													+			$ \rightarrow $				_			_			_	_	_	_	
Inclusion / Exclusion criteria	×		×		_				$ \rightarrow $					+		_	$ \rightarrow $				_			_	_		_	_	_		
Relevant med. hist. / Current med. cond.	x		×						+					+		_	$ \rightarrow $			$ \rightarrow $	_				_		_	_	_	_	
Demography	×																														
Prior / concomitant medication(s)					_		_	_		_		_	_				 	_	-		_	_			_			_			
Hepatitis B and C screen and HIV screen	×				-			_						+			+				-						_	_	_	_	
Quantiferon TB test	×				-		-														-				-		-		-	-	
Alcohol test, drug screen	x		X					×				×			2	<			×				X					X			
FSH test (temales only)	×							-																							
Pregnancy test (in serum, females only)	×				-									+		-	+				-				-				_	-	×
Pregnancy test (urine, females only)			×"		_		>			_		X)				X				X	_			х	x			
Physical examination	×		X		_		>					×	_)	<		_	×		_		×	_	_		×	×	×	×	×
Joint Range Of Motion	x		X				>	C X				X		+)	<	$ \rightarrow $		X		_		X				x	X	X	х	×
Body height	×																														
Body weight	×		X									X)	<			X		_		X		_		×	×	x	х	×
Vital Signs: Body temperature, Blood pressure, Pulse	×		×		X^2	X			X2		×	×	X^2		X		K ²	X >		X	2	XX	×	- X ²	×	×	×	×	×	×	×
ECG evaluation ³	X		X	×		X	>	(X		X		X		X	2			×	X			x	X		X		×	X	x	X	×
Hematology and Clinical chemistry 13	×		X11					< X				×)	<			×				×				×	×	×	×	×

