- For samples drawn on Day 1 there is $a \pm 15$ min window.
- For samples drawn after Day 1, there is a ± 6-hour window (based on T=0 dosing start time).

Confidential

Visit windows

- From Day 1 to Day 15 visits should be conducted as scheduled.
- Day 15 and Day 28 there is $a \pm 3$ day visit window.
- From week 8 (Month 2 visit) to week 28 (Month 7 visit) there is $a \pm 5$ day window.
- At week 12 visit, the ± 5 days window allows the site to perform week 12 MRI and receive information on potential dose escalation before planned dosing day.
- For all follow-up visits until End Of Study visit, there is $a \pm 8$ days window.

Patients who prematurely withdraw from the study for any reason should be scheduled for a visit as soon as possible, at which time all of the assessments listed for the final visit 777 will be performed.

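### SAP 7.1.2's pooled Part B* repeated-measures ANCOVA uses visit as its time factor, but after week 12 one visit number covers scans 4 to 20 weeks apart in Parts B and C, and visit 777 spans 32 weeks

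*SAP*

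**What the plan says.** SAP 7.1 defines Part B* as "MCS110 data only, by including data starting from the 1st dose of MCS110 in all treatment groups of Parts B and C". SAP 7.1.2 then fits a repeated-measures ANCOVA of log ratio to baseline on these data, to describe the time course of tumor volume. Its time term is visit: "The model will include log tumor volume at baseline and visit as fixed effects". An estimate and 95% CI are reported at each visit, and a baseline-adjusted curve is plotted over time.

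The only alignment rule covers Part B patients who had placebo first: "resetting the tumor volume at week 4 as baseline for patients in treatment group 2 and the visit number will be adjusted accordingly". Nothing maps Part B visits to Part C visits, and no analysis windows are given.

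Protocol 9.4.4 has the parent model for Part B alone, with a different time term: "The model will include tumor volume at baseline and assessment time (in month) as fixed effects". It says the model may be fitted; the SAP says it will be.

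Two further rules affect the last visit. Under the Part C adult schedule for Amendment 07, patients already past visit 14 or 15 "need to come back to the site within 1 month for an end of study visit". Protocol section 6 brings early withdrawals in as soon as possible, "at which time all of the assessments listed for the final visit 777 will be performed".

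**The concern.** A visit factor is a sound time axis when all pooled patients share one schedule. Here they do not. Part B follow-up is every 3 months. Part C has visits at weeks 24, 28, 40 and 56, then ends at week 72 (Amendment 7) or continues to week 104 (Amendment 6). If visit means visit number, one factor level joins scans taken at different times and at different distances from the last dose.

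The stake is how the curve after week 12 is read. That is where durability of response and regrowth off drug would be judged. The listed fixed effects contain no term for Part, dose level, number of doses or time off drug, so nothing in the model separates the mixed groups. Neither Part is small enough to ignore: Protocol section 1, under Study CMCS110X2201, reports 11 patients exposed in Part B and 18 in Part C.

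**Working it through.** **Inputs.** Visit-to-week maps come from the protocol's assessment schedules B1, B2, Part C adults (Amendments 07 and 06) and Part C adolescents. Where the extracted Part C tables are broken, I checked weeks against study days with day = 7 × week + 1: 20/141, 24/169, 28/197, 40/281, 56/393, 72/505 and 104/729 all fit.

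**Step 1: apply the SAP's own realignment.** For schedule B1 (placebo first), subtract one visit number and 4 weeks. Visits 9 to 15 at weeks 24, 28, 40, 52, 64, 76, 88 become visits 8 to 14 at weeks 20, 24, 36, 48, 60, 72, 84. End of study moves from week 100 to week 96. This equals schedule B2 at every visit, so the rule works within Part B.

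**Step 2: compare Part B with Part C, in weeks since first MCS110 dose.**

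| Visit | Part B | Part C | Gap (weeks) |
|---|---|---|---|
| 5, 6, 7 | 4, 8, 12 | 4, 8, 12 | 0 |
| 8 | 20 | 16 | 4 |
| 9 | 24 | 20 | 4 |
| 10 | 36 | 24 (no MRI marked) | no mixing |
| 11 | 48 | 28 | 20 |
| 12 | 60 | 40 | 20 |
| 13 | 72 | 56 | 16 |
| 14 | 84 | 72 (Amendment 6 only) | 12 |
| 15 | none | 88 (Amendment 6 only) | no mixing |
| 777 | 96 | 72 (Amendment 7) or 104 (Amendment 6) | 24 or 8; full range 104 − 72 = 32 |

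Visit 777 also collects call-back and early-withdrawal scans, which have no fixed week.

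**Step 3: weeks since last dose.** Assume no dosing delays, so the last dose is at week 12 (four doses) or week 20 (six doses).
- Visit 11: Part B 48 − 12 = 36 or 48 − 20 = 28; Part C with six doses 28 − 20 = 8, which is the primary-endpoint scan.
- Visit 12: Part B 60 − 12 = 48 or 60 − 20 = 40; Part C with six doses 40 − 20 = 20.
- Visit 8: Part B four-dose patients 20 − 12 = 8; six-dose Part C patients are still being dosed.

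**Step 4: what a visit-11 level would represent.** If all 11 and 18 exposed patients were still scanned, the mean scan time would be (11 × 48 + 18 × 28)/29 = 1032/29 = 35.6 weeks, a time at which neither Part has a scan.

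**Step 5: the reverse problem.** After week 20, Part B scans fall at weeks 24, 36, 48, 60, 72, 84, 96 and Part C scans at 28, 40, 56, 72, 88, 104. Only week 72 is shared. It is visit 13 in Part B, visit 14 in Part C under Amendment 6 and visit 777 under Amendment 7. The visit factor therefore splits the one follow-up time the Parts have in common.

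**The case against.** **Visit may mean scheduled time point.** The model's stated aim is a time course, its output is plotted over time, and SAP 7.1 speaks of adjusting assessment time-points for Part B*. This reading is possible and would remove the clash. Against it, 7.1.2 dropped the protocol's months and speaks of adjusting the visit number. Sections 4 and 9 of the SAP are not visible, so a definition could sit there; if so, 7.1.2 needs a cross-reference.

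**The visit numbers are labels.** The schedules say the visit structure is for programming, and Part B carries a second set of numbers. Using that set does not help. B1 follow-up becomes 109 to 115 with 778 at the end, B2 becomes 208 to 214 with 779, and Part C stays at 8 to 15 with 777. Follow-up would then share no levels, even within Part B. Even one B2 week-20 scan would carry one of two labels: "Visit 208 (Part B2) will not be performed if patients had visits optional dosing visits 215 and 216 (schedule B2".

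**Stronger readings that the documents do not support.** A reader might infer that every visit estimate is affected. Visits 5 to 7 agree, visit 10 has no Part C MRI marked, and visit 15 is Part C only. A reader might infer that nothing else models the multiple-dose time course. The dose-time-response model in the same SAP section uses each patient's dose amounts and dose times, treats time as continuous and allows for dependence within a patient. A reader might also infer damage to the primary results. The Part A* Bayesian analysis stops at week 4, Part C dose decisions use the week-12 scan, and the waterfall plot and times to ablation do not use this model.

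**Conclusion.** The point holds as a moderate error in a supportive, estimation-only analysis. As written, the Part B* ANCOVA gives estimates at visits 8, 9, 11, 12, 13, 14 and 777 that mix different times since first dose. The gap between Parts is 4 to 20 weeks at the numbered visits, largest at visits 11 and 12, and visit 777 has a scheduled range of 32 weeks. The estimates, intervals and curve at those visits have no defined time.

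This rests on reading visit as the scheduled visit number, which the SAP's wording favors but does not define, and on the scheduled weeks. The time-off-drug figures also assume undelayed dosing.

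**What to change.** In SAP 7.1.2, Part B*:
- Replace visit with time since first MCS110 dose, as in Protocol 9.4.4, either as scheduled week or as continuous actual time.
- Assign end-of-study, call-back and early-withdrawal scans by actual day, not as visit 777.
- After week 20, estimate and plot Parts B and C separately, or include a Part-by-time term. Otherwise the pooled curve alternates between Part B, all at 10 mg/kg, and Part C, which mixes doses.
- If windows are used, make each narrow enough to hold one scheduled scan per patient, or state which scan is kept. A window of weeks 48 to 60 would hold two Part B scans, and weeks 84 to 104 would hold two in Part B and two in Part C under Amendment 6.

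The cost is one derived time variable, a wording change and fewer patients per late time point; no new data are needed. SAP 1.2 counts a change of statistical model as minor, so a note to file can record it. Time since first dose leaves an 8-week difference in time off drug (20 − 12) between four-dose and six-dose patients, which should be noted beside the curve.
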